# **Clinical outcomes**

### **Microbiome analysis**

Whole population DNA will be extracted directly from vaginal and urine samples for both 16S and shotgun-metagenomic sequencing. Sequenced reads will be mapped to the human genome, in order to remove any host DNA contamination. For both 16S and shotgun-metagenomic sequences, reads not aligning to the human genome will then be assigned taxonomic grouping using the Kraken software package. Abundance of taxa/species will be determined by calculating counts per million reads. Changes in microbiome composition will then be determined by comparing the Shannon's diversity index between treatments and sampling timepoints using ANOVA (Yang et al, 2016).

This type of analysis will allow us to further identify the unique microbiome that exists in the urinary bladder. This would not be possible with standard urinary cultures, as without an abundance of 1-2 species, urinary cultures are limited in identifying an existing low count microbiome. This study will add to the microbiome literature in several ways. This type of analysis has not been described using vaginal cultures in patients with rUTI. Furthermore, analysis of change with treatment has not been described in this population as well, from both the urinary and vaginal microbiome perspective. Understanding this information has potential to develop new therapies that may help in treating menopausal women with rUTI.

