Fractional CO2 LASER vaginal therapy has recently been studied for the treatment of GSM. LASER therapy is currently commercially available and has FDA clearance for use in gynecology. Current evidence shows that with treatment, histologic changes of the vaginal epithelium have shown regeneration to a premenopausal state, along with subjective improvement in GSM symptoms and sexual function. Using LASER therapy, Zerbinati et al described response by the vaginal epithelium with thickening, superficial shedding and renewing of stratified epithelium, which was maintained 2 months after treatment.[4] Athanasiou et al also described the impact of LASER therapy on the vaginal flora, decreasing the vaginal pH to 4.7 (p<0.001) and increasing the Lactobacillus colonies from 30% to 79%.[5] Based on the impact this promising new regenerative therapy has on the vaginal epithelium and microbiome, we anticipate this may have a positive impact on women with rUTI.

- We therefore hypothesize that fractional CO2 LASER vaginal therapy is non-inferior to topical vaginal estrogen therapy for the treatment of rUTI.
  a. Primary Outcome: Improvement in recurrence of culture positive UTI
- 2. We also hypothesize that LASER therapy will improve the urinary and vaginal microbiome, decreasing the uropathogenic presence and increasing Lactobacillus.
  - a. Measurement 1: The number of UTI with UPEC isolated from patients
  - b. Measurement 2: The pH of the vagina as a proxy for presence of Lactobacillus sp.
  - c. Measurement 3: Categorize vaginal and urinary microbial communities

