# Vaginal Estrogen Protocol

Women randomized to vaginal estrogen therapy will be offered vaginal cream. Two FDA approved formulations exist and patients will be offered the choice between the two, which may also be dependent on their insurance formulary preference.

- 1. Conjugated estrogen (Premarin): 0.5 gm per vagina twice weekly
- 2. Estradiol (Estrace): 1gm per vaginal twice weekly

**Specific Aim 1:** Evaluate the number of culture positive, symptomatic UTI in women following randomization to vaginal estrogen and vaginal LASER therapy.

Methods: Following randomization and treatment initiation, patients will be monitored for recurrence of UTI. Patients will be encouraged to call the treating physician for treatment antibiotics according clinical judgment. Standard urine cultures will be obtained along with information about what type of antibiotic treatment was administered. Validated questionnaires will also be collected to monitor symptoms of GSM and also of urinary incontinence symptoms (Appendix A and B). Patients will be followed for 6 months with evaluations at baseline, 4 months, and 6 months.

**Specific Aim 2:** Characterize the urinary and vaginal microbiome at baseline and at 4 months of patients in each group.

Methods: Baseline vaginal and catheterized urine samples will be collected along with samples at 4 months. Standard catheterized urine cultures will be performed and if symptomatic, treated appropriately (per Aim 1). Microbiome of urine and vaginal environments will then be analyzed using 16S ribosomal DNA sequencing along with shotgun metagenomics. For this study, we will perform sequencing and metagenomics on the first 16 patients in each arm (32 patients total). The remaining collection will be biobanked for future analysis. These techniques will allow us to measure the abundance of different bacteria, but also evaluate the genetic variation and evolutionary effect from treatment. This will also allow us to evaluate for the differences in the microbiome between responders and non-responders in each treatment arm, considering factors such as UTI, symptoms, pH, etc.

Vaginal Estrogen arm	Baseline	4 months	6 months (if can be completed within the funding period)
Informed consent	X		
Vaginal pH	X	X	Х
Vaginal swab collection	X	X	X (banked)
Urine collection	Х	Х	X (banked)
MESA questionnaire	X	Х	Х
DIVA questionnaire	Х	Х	X

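### Aim 2 urine sequencing removes only human reads, so background bacterial DNA is counted as bladder taxa and can bias Shannon's index in either direction

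*Combined protocol and SAP*

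**What the plan says.** The Microbiome analysis section (under Clinical outcomes) sets out the pipeline in order:

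- Removal of reads: "Sequenced reads will be mapped to the human genome, in order to remove any host DNA contamination".
- Classification: "reads not aligning to the human genome will then be assigned taxonomic grouping using the Kraken software package".
- Abundance: "Abundance of taxa/species will be determined by calculating counts per million reads".
- Endpoint and test: "comparing the Shannon's diversity index between treatments and sampling timepoints using ANOVA".

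The same section justifies sequencing on the ground that "urinary cultures are limited in identifying an existing low count microbiome". Specific Aim 2 gives the samples: "Baseline vaginal and catheterized urine samples will be collected along with samples at 4 months". Sequencing covers the first 16 women in each arm, 32 in all. Aim 2 also plans to compare responders with non-responders within each arm.

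Nowhere do the documents mention extraction blanks, catheter or collection blanks, a filter for background taxa, a measurement of bacterial load, or a rule for allocating samples to sequencing batches.

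**The concern.** Contamination is considered, but only contamination of human origin. Bacterial DNA also enters a sample from extraction reagents, the catheter and handling. Mapping to the human genome leaves those reads in place, and the classifier then assigns them to taxa as though they came from the bladder.

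In a sample rich in bacteria this hardly matters. In a low-count sample it can, because a roughly fixed amount of background makes up a larger share of the reads as the true load falls. Scaling to counts per million discards total load, so the analyst cannot see this happening.

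Load may well change during the trial: treatment is meant to reduce uropathogens, and symptomatic infections are treated with antibiotics. A difference in Shannon's index between visits, between arms, or between responders and non-responders could then reflect load or batch and not the community itself.

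**Working it through.** **Inputs.** The documents give the pipeline, the low-count description and the number sequenced (16 per arm, 32 in all). They give no bacterial load, background amount or number of taxa, and no figure for Shannon's index, so there is no plan figure to reproduce. Everything numerical below is assumed:

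- true community of 5 taxa at 70, 15, 8, 4 and 3%, unchanged throughout;
- background amount K, fixed, and true load B, varying, in the same units;
- three types of background: 20 even taxa not in the true community; 3 even taxa not in it; or the dominant true taxon itself.

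**Formulas.** The background share of reads is c = K/(B + K). When background and true taxa do not overlap,

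H(c) = −c ln c − (1 − c) ln(1 − c) + (1 − c)·Ht + c·Hb,

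where Ht and Hb are the Shannon indices (natural log) of the true and background communities. H rises with c up to c* = e^Hb / (e^Hb + e^Ht) and falls beyond it.

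**Step 1: true index.** Ht = 0.250 + 0.285 + 0.202 + 0.129 + 0.105 ≈ 0.97, so e^Ht = 2.64.

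**Step 2: share.** With K = 1,000, c is 1% at B = 100,000, 9% at 10,000, 50% at 1,000, 91% at 100 and 99% at 10. Only the ratio B/K matters. With K = 100 or K = 10,000 the same columns apply at loads ten times lower or ten times higher.

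**Step 3: index at a 50% share.**

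- 20 even taxa, Hb = ln 20 = 2.996: 0.693 + 0.485 + 1.498 = 2.68.
- 3 even taxa, Hb = ln 3 = 1.099: 0.693 + 0.485 + 0.549 = 1.73.
- Dominant taxon: the mixture is 85, 7.5, 4, 2 and 1.5%, so H = 0.138 + 0.194 + 0.129 + 0.078 + 0.063 = 0.60.

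**Step 4: full range** (true value 0.97 in every cell).

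| Background | c = 1% | 9% | 50% | 91% | 99% |
|---|---|---|---|---|---|
| 20 even taxa | 1.05 | 1.46 | 2.68 | 3.12 | 3.03 |
| 3 even taxa | 1.03 | 1.29 | 1.73 | 1.39 | 1.15 |
| Dominant taxon itself | 0.96 | 0.91 | 0.60 | 0.16 | 0.02 |

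The turning points are c* = 20/(20 + 2.64) = 0.88 and 3/(3 + 2.64) = 0.53. For a more diverse true community the index can fall below its true value: with 20 even true taxa (Ht = 3.00) and 3 even background taxa, it is 3.13 at a 9% share, 2.74 at 50% and 1.58 at 91%.

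**Step 5: what a visit comparison would see.** Suppose load falls tenfold between baseline and 4 months, moving c from 9% to 50%. The apparent change is 2.68 − 1.46 = +1.22 with 20 background taxa, 1.73 − 1.29 = +0.44 with 3, and 0.60 − 0.91 = −0.31 if the background is the dominant taxon. The real change is zero in all three cases.

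**The case against.** A reader might infer that background DNA raises Shannon's index whenever load falls, so that an effective treatment would look as if it increased diversity. The documents do not support this. The sign depends on the background taxa, their overlap with the true community and the size of the share; even with 20 background taxa the index turns down from 3.12 to 3.03 at very high shares. Nor does hypothesis 2 predict a fall in total load. It predicts "decreasing the uropathogenic presence and increasing Lactobacillus", which is a replacement of taxa, and it states no direction for Shannon's index. A false rise would therefore not by itself confirm the hypothesis.

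Other points in the plan's favour have weight:

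- The arms are randomised, so a shared background creates a between-arm difference only if load or processing differs by arm. The baseline to 4-month comparison is more exposed.
- Catheterised collection limits vaginal and skin carry-over, though not reagent or catheter DNA. Vaginal samples are not described as low count.
- Two of the three hypothesis 2 measurements, infections with UPEC and vaginal pH, do not rest on sequencing.
- The laboratory, or the 2016 method the plan cites, may already include blanks. The documents do not say, so absence cannot be asserted.

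These limit the scope and rule out a claim about direction. They do not remove the point. The written pipeline runs from raw reads to the test with no step for bacterial background, and blanks run in the laboratory would not change the analysis unless the plan says how they are used.

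**Conclusion.** The concern holds as a possible bias of unknown size and sign in the Aim 2 urine analysis. Followed as written, the pipeline counts background bacterial DNA as bladder taxa, in a share that grows as load falls. Shannon's index can then move without any change in the community if load or batch differs by visit, arm or responder status. A rise is the usual result when one species dominates and the background is diverse; a fall occurs in other cases.

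At a 50% share, an index truly equal to 0.97 reads anywhere from 0.60 to 2.68 across the three backgrounds tried; at a 1% share it reads 0.96 to 1.05. Where this trial's samples would lie in that range cannot be known from the documents.

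The point affects urine sequencing in 32 women and leaves the primary comparison of culture-positive UTI untouched. It is a worthwhile, inexpensive improvement and no threat to the trial's main conclusion.

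**What to change.** Amend the Microbiome analysis section as follows.

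1. Carry extraction blanks and unused-catheter or collection blanks through every sequencing batch.
2. Process each woman's baseline and 4-month samples in the same batch, with both arms mixed within batches.
3. Remove background taxa by a prespecified prevalence or frequency rule before computing abundance and Shannon's index.
4. Report the Shannon comparison before and after removal.
5. Keep samples that resemble the blanks in the main comparison. Excluding them selects on bacterial load, which treatment may change, and could deplete one arm or visit. Flag them, report their number by arm and visit, and drop them only in a sensitivity analysis.

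If the laboratory already runs blanks, items 1 and 2 may need only a sentence each; the rule in item 3 still has to be written down before the data are seen.

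The cost is a few extra blank libraries per batch and one filtering step, with no added patient procedure. The downside is that some genuine low-abundance taxa may be filtered out, which the before-and-after report would show. The blanks should be arranged before samples are processed, since they cannot be reliably recreated afterwards. Collection blanks should also be stored with the banked samples.

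### Sequencing abundance is a share of reads and its only test, on Shannon's index, has no direction, so this analysis cannot by itself show that uropathogens decreased

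*Combined protocol and SAP*

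**What the plan says.** The second hypothesis, at the end of the Background, is that LASER therapy will improve the urinary and vaginal microbiome by "decreasing the uropathogenic presence and increasing Lactobacillus". Three measurements follow:

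- Measurement 1: "The number of UTI with UPEC isolated from patients".
- Measurement 2: "The pH of the vagina as a proxy for presence of" Lactobacillus.
- Measurement 3: a classification of the vaginal and urinary communities. This is the one that rests on sequencing.

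Under Specific Aim 2 the plan says of sequencing: "These techniques will allow us to measure the abundance of different bacteria". Microbiome analysis defines the unit: "Abundance of taxa/species will be determined by calculating counts per million reads". It then names one test: "Changes in microbiome composition will then be determined by comparing the Shannon's diversity index between treatments and sampling timepoints using ANOVA". It names no total-load measurement, spike-in standard, log-ratio or other compositional method, and no test for a single taxon.

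Sequencing is limited to the first 16 women per arm. The visit schedules list urine collection at baseline and 4 months in both arms. Specific Aim 2 adds, for these samples, "Standard catheterized urine cultures will be performed", and Data Collection says that culture results will be documented in detail. The Statistical Analysis section covers UTI recurrence overall, the questionnaires and vaginal histology. It gives no analysis of UPEC infections or of uropathogens on the scheduled cultures.

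**The concern.** Counts per million have a fixed sum. When the Lactobacillus share rises, the combined share of everything else has to fall, whether or not the amount of any other organism has changed. Hypothesis 2 predicts exactly this rise. The second half of the hypothesis, a decrease in uropathogens, is therefore confounded with the first half on the scale chosen for abundance.

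The named test does not help. Shannon's index describes evenness and richness and does not record which organism is dominant. A statement about the direction of change in uropathogens would have to be drawn from the counts per million, and the plan sets no limit on how these may be interpreted. At stake is whether a lower uropathogen share after treatment could be presented as a benefit distinct from the rise in Lactobacillus.

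**Working it through.** **The plan's own figure.** The plan gives no sample size or power for the microbiome endpoint. The only design figure is the total of 94. With 16% recurrence in both arms, a margin of 20 percentage points, 80% power and a one-sided 5% level (the plan does not state the sidedness):

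- n per arm = (1.645 + 0.842)² × 2 × 0.16 × 0.84 / 0.20² = 41.6, so 42.
- With 10% dropout: 42 / 0.9 = 46.7, so 47 per arm and 94 in total. This reproduces the plan.
- Evaluable women: 2 × 42 = 84, against 2 × 16 = 32 sequenced.

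**Dilution on the counts-per-million scale.** Let s be the baseline Lactobacillus share and f the fold rise in its load, with all other loads constant. Total load becomes 1 − s + s·f times its baseline, so the count per million of an unchanged taxon changes by 1 / (1 − s + s·f) − 1.

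*Illustration.* The Background cites a study as "increasing the Lactobacillus colonies from 30% to 79" (per cent). The text speaks of colonies, so treating these figures as read shares is an assumption.

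- Share left for all other taxa: 1 − 0.30 = 0.70 before and 1 − 0.79 = 0.21 after.
- Ratio 0.21 / 0.70 = 0.30, a 70% fall for each other taxon with no change in amount (for example 100,000 to 30,000 per million).
- Implied total load: 1 / 0.30 = 3.33-fold. Implied Lactobacillus load: 0.79 × 3.33 / 0.30 = 8.8-fold.

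*Range* (assumed s and f):

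| Baseline share s | f = 1.5 | f = 10 |
|---|---|---|
| 5% | −2% | −31% |
| 30% | −13% | −73% |
| 60% | −23% | −84% |

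*The sign can be wrong.* Take a uropathogen at 10% of baseline load that truly doubles while Lactobacillus rises 8.8-fold from 30%. Its share becomes 0.2 / (0.3 × 8.78 + 0.7 + 0.1) = 0.2 / 3.43 = 5.8%, a fall from 10%.

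*The fall is not inevitable for one taxon.* With Lactobacillus going from 30% to 79% and other taxa from 60% to 11%, a uropathogen stays at 10% throughout.

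**Shannon's index.** For shares of 79%, 11% and 10%, H = −(0.79 ln 0.79 + 0.11 ln 0.11 + 0.10 ln 0.10) = 0.659. The value is the same whether Lactobacillus or the uropathogen holds the 79%.

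**Which log-ratio.** In the 70% illustration, take a uropathogen that goes from 10% to 3% with its load unchanged. The other non-Lactobacillus taxa then go from 60% to 18%.

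- Uropathogen to Lactobacillus: 10/30 = 0.333 becomes 3/79 = 0.038, an 89% fall. This is a larger artefact than in the counts per million.
- Uropathogen to other non-Lactobacillus taxa: 10/60 = 0.167 and 3/18 = 0.167. It does not change.

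**The case against.** A reader might infer that uropathogen counts per million must fall whenever Lactobacillus rises, and that the trial has no separate way to show a decrease. The documents support neither. Only the combined non-Lactobacillus share has to fall, and the 10%-to-10% case shows that a given uropathogen can keep its share. Measurement 1 is based on isolates and vaginal pH is not a read count, so both directions of the hypothesis have an instrument that does not depend on read shares.

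That objection stands and narrows the point to the sequencing data. It does not remove the point. Measurement 1 counts infections, not presence at 4 months. The Background attributes the great majority of infections to E. coli, so it largely overlaps the primary outcome.

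It can also be said that the plan names no per-taxon test, so a mistaken claim about uropathogen shares is only a possibility. This is correct: the documents do not say that such a fall will be reported as a benefit. But then no stated sequencing analysis addresses the direction of Hypothesis 2 at all.

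Finally, culture answers a different question. Microbiome analysis itself says that culture is poor at finding low-count organisms. The move from 32 to about 84 women is therefore a change of endpoint and not a gain in precision on the same one. The colony thresholds under Inclusion Criteria define eligibility, and the plan does not promise colony counts at 4 months. Culture can complement sequencing but cannot replace it.

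**Conclusion.** The point holds for the sequencing analysis as written, which cannot separate a true fall in uropathogens from dilution by Lactobacillus. The possible artefact is 70% in the illustration and about 2% to 84% over the assumed range. These figures rest on constant loads for all other taxa and on assumed baseline shares and fold rises. The 70% also treats a reported percentage of vaginal colonies as a read share. It should not be read as the artefact that the plan itself predicts, nor carried over to urine.

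The consequence is modest: a secondary aim, 32 sequenced women, no powered microbiome endpoint and no effect on the primary outcome. The change is still worth making, because the planned cultures would give Hypothesis 2 a directional analysis that it now lacks.

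**What to change.** 1. State in Microbiome analysis that counts per million support relative conclusions only, and that no absolute decrease in vaginal uropathogens will be claimed.
2. If a sequencing contrast is wanted, prespecify the log-ratio of uropathogens to the other non-Lactobacillus taxa, and do not use Lactobacillus as the denominator. This removes the dilution by Lactobacillus but is still relative: if uropathogens and the other taxa decline together, the ratio does not move.
3. For urine, add a comparison between arms of uropathogen presence on the 4-month catheterized culture, and of colony count where reported, adjusted for the baseline culture. Use all evaluable women (about 84 if cultures are done in everyone, as the schedules suggest). Present it as a complement to sequencing and state that culture misses low-count organisms.

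The cost is some SAP wording and one extra regression on data already planned. The vaginal conclusion becomes narrower, and the added urine endpoint covers only culturable uropathogens.

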# Methods

We propose a randomized controlled trial to evaluate the clinical difference between the LASER and topical vaginal estrogen in treating patients with rUTI. We expect to enroll 94 patients, to power this study to 80% with type I error of 5%, expecting a recurrence in UTI of 16% and non-inferior margin of 20%. This is accounting for a 10% drop out rate. While this clinical margin is wide, this project will provide us with ample data to apply for external funding, along with a wealth of microbiome data to evaluate in Aim 2. Menopausal women with rUTI will be recruited from the Departments of Urology and Gynecology. If they meet inclusion criteria, they will be randomized to treatment of topical vaginal estrogen or LASER therapy. LASER therapy will be applied 6 weeks apart for a total of 3 treatments. Topical vaginal estrogen will be prescribed per the patient's formulary and preference. Patients will be monitored for recurrence of culture positive UTI.

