# **Statistical Analysis**

The 4-month rUTI prevalence and 6-month rUTI prevalence will be estimated using binomial method and compared between the two groups using Chi-square test or Fisher's exact test when applicable. The 6 month rUTI recurrence rate will be estimated using Poisson method and compared between the two groups using GEE method.

Overdispersion will be evaluated and if presented, negative binomial method will be used to estimate the rUTI recurrence rate.

Time to first recurrent UTI will also be compared between the two groups using log-rank test.

The MESA responses, DIVA responses and vaginal histology changes over time will be summarized and compared between the two groups using general linear mixed model or generalized linear mixed model when appropriate.

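### The microbiome ANOVA names no within-woman term, baseline adjustment or treatment contrast; a baseline-adjusted ANCOVA at 4 months would settle this at no cost (Aim 2 only)

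*Combined protocol and SAP*

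**What the plan says.** Specific Aim 2 is to "Characterize the urinary and vaginal microbiome at baseline and at 4 months of patients in each group". Its methods make the data paired: "Baseline vaginal and catheterized urine samples will be collected along with samples at 4 months". On numbers, the plan says "we will perform sequencing and metagenomics on the first 16 patients in each arm (32 patients total"), with the remaining samples stored for later work. Each specimen type therefore yields 32 × 2 = 64 Shannon values from 32 women.

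The only comparative microbiome test is in the Microbiome analysis section under Clinical outcomes: "comparing the Shannon's diversity index between treatments and sampling timepoints using ANOVA", followed by a literature citation. The section does not say whether the ANOVA is ordinary or repeated-measures, whether arm, time or arm-by-time is the test of interest, or whether urine and vaginal samples are analysed separately.

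The Statistical Analysis section does name methods for correlated data for other outcomes. MESA, DIVA and vaginal histology over time are to be "compared between the two groups using general linear mixed model or generalized linear mixed model when appropriate", and the UTI recurrence rate is to be compared by GEE. The microbiome is not in either list.

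**The concern.** Two samples from one woman are likely to be positively correlated. An analyst who follows the text literally could enter arm and time as factors and let the software treat all 64 values as independent. The arm comparison would then be too liberal and the comparison of change too conservative.

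A second gap remains whichever ANOVA is used. With both time points in the model, the arm main effect averages a pre-treatment sample with the 4-month sample, so a true 4-month difference d appears as d/2. The plan does not say that arm-by-time, or the 4-month difference, is the comparison that answers the treatment question. At stake is whether Aim 2 reports a spurious arm difference or misses a real one, and whether the choice of model is left until the data have been seen.

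**Working it through.** **The plan's own figure.** The documents give no power, SD or effect size for the microbiome test, so there is none to reproduce. The one sample-size figure is in Methods ("We expect to enroll 94 patients") and belongs to the primary outcome. With 16% recurrence assumed in both arms, a margin of 20 points, 80% power and one-sided 5%: n = (1.645 + 0.842)² × 2 × 0.16 × 0.84 / 0.20² = 41.6, so 42 per arm, 84 in total, and 84 / 0.90 = 93.3, rounded up to 94. It reproduces, and nothing below affects it.

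**Inputs.** From Specific Aim 2: 16 women per arm, two time points. Assumed: within-woman correlation ρ of 0.3, 0.5 or 0.7, normal outcome, equal variances, complete pairs, two-sided 5% tests, and a true 4-month difference of 1 SD.

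**Standard errors, in SD units, n = 16 per arm.**
- Arm main effect: ordinary ANOVA uses √(1/n) = 0.250. The true value is √((1+ρ)/n) = 0.285, 0.306, 0.326 at ρ = 0.3, 0.5, 0.7. The stated error is too small.
- Arm-by-time: ordinary ANOVA uses √(4/n) = 0.500. The true value is √(4(1−ρ)/n) = 0.418, 0.354, 0.274. The stated error is too large by a factor 1/√(1−ρ), which is 41% at ρ = 0.5 (20% to 83%).
- 4-month values only: √(2/n) = 0.354 at any ρ.
- ANCOVA on baseline (large-sample form): √(2(1−ρ²)/n) = 0.337, 0.306, 0.252.

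**Simulated error and power at ρ = 0.3 / 0.5 / 0.7.** Ranges within a cell are results from separate simulation runs.

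| Reading of the plan | True error at nominal 5% | Power, 1 SD at 4 months |
|---|---|---|
| Ordinary ANOVA, arm main effect | 8.3–8.5% / 10.7–11.1% / 13.2–13.3% | estimates d/2, not d |
| Ordinary ANOVA, arm-by-time | 2.0–2.1% / 0.6–0.7% / 0.1% | 50–51% throughout |
| Repeated-measures ANOVA, arm-by-time | 5% | 64% / 78% / 94% |
| Repeated-measures ANOVA, arm main effect | 5% | 40% / 35% / 32% |
| Arms compared at 4 months only | 5% | 78% throughout |
| ANCOVA, 4-month value on arm and baseline | 5% | 81% / 87% / 96% |

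A one-way ANOVA over the four arm-by-time cells has error of about 4% and rejects about 82% of the time in this scenario. Its omnibus test also rejects when both arms change equally, so it does not test the treatment difference.

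At ρ = 0 the ordinary ANOVA is undistorted, and the formula gives ANCOVA no advantage over the 4-month comparison.

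**The case against.** A reader might infer that the plan uses an ordinary ANOVA, treats paired samples as independent, and so has the wrong error rates. The documents do not support that. They say only ANOVA. The term covers repeated-measures ANOVA, naming treatment and sampling time as factors fits that reading, and the cited source is not available to settle it. The team names GEE and mixed models elsewhere, so it knows about correlated data. Under a repeated-measures reading or a comparison at 4 months, the type I error is correct. This part of the objection stands.

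A reader might also set 51% power against 87% as the price of ignoring the pairing. That mixes two changes. At ρ = 0.5, adding a within-woman term takes power from about 51% to 78%; the further step to 87% comes from adjusting for baseline instead of analysing change.

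Finally, this is a 32-woman substudy with no power claim, and its data could be analysed properly after collection. That limits the importance of the point. It does not remove the gap: the plan still names no contrast, and the readings it permits give materially different answers.

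**Conclusion.** The finding is under-specification, with a better method available at no cost. The samples are paired, and the plan gives no within-woman term, baseline adjustment or treatment contrast. Distorted error rates follow only if the ANOVA is run as an ordinary two-way analysis.

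On every reading that isolates the treatment difference, ANCOVA has at least as much power across the assumed range. Against the better of repeated-measures ANOVA and the 4-month comparison, the gain is about 3 points at ρ = 0.3 (81% against 78%), 9 at 0.5 (87% against 78%) and 2 at 0.7 (96% against 94%). These figures rest on the assumed correlation, normality, complete pairs and a 1 SD effect, none of which the documents supply. The consequence is confined to Aim 2; the primary outcome and the total of 94 are unaffected.

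**What to change.** In the Microbiome analysis section, replace the ANOVA with an ANCOVA of the 4-month Shannon index on arm and baseline Shannon index, fitted separately for urine and vaginal samples, and name the LASER-minus-estrogen difference at 4 months as the test.

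If a mixed model with a woman-level effect is preferred, for consistency with the Statistical Analysis section, state that baseline means are constrained equal across arms. Without that constraint, a random-intercept model with arm, time and arm-by-time reproduces the analysis of change (78% power at ρ = 0.5), not the ANCOVA.

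Within-arm change is a stated interest of Aim 2 and may be reported with a paired analysis. It should not be read as a treatment effect, because there is no untreated arm.

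The cost is about one sentence in the plan. The baseline sample is already collected, so no new data, visits or sequencing are needed.
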